#### **8.4.3 Prohibited concomitant medications.**

Any treatment that may interfere with the IMP taken during the study. This includes treatment from Day -1/Baseline (Visit 2) until End of Study or Early Termination (except if needed for care and treatment of the subject during the study per Investigator discretion).

The **Error! Reference source not found.** in APPENDIX C provides a listing of prohibited medications; however, it is not a comprehensive list of all restricted medications, supplements, and other therapeutics. Final list with prohibited medications will be identified on a case-by-case basis by a Sponsor medical review of the concomitant medications.

### **8.5 EXPOSURE TO INVESTIGATIONAL MEDICAL PRODUCT (IMP)**

Exposure information will be expressed in terms of treatment duration (days) derived as the number of days from the date of first dose of randomized treatment received (Study treatment start date) to the date of the last dose received (Study treatment end date), inclusive (section 11.1.1) according to the formula:

Study treatment end date - Study treatment start date +1.

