13.4 Treatment Exposure

Exposure to randomized treatment for the SAF set during the double-blind treatment period will be summarized in terms of treatment duration, calculated as the number of days from the date of first dose of randomized treatment received to the date of the last dose received, inclusive. Descriptive statistics (n, mean, SD, minimum, median, and maximum) will be presented by treatment group for treatment exposure. The total number of doses received by a subject during the double-blind treatment period will be summarized by treatment group for the SAF.

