### **8.6 COMPLIANCE WITH STUDY TREATMENT**

The IMP will be administered at the clinic under supervision of study personnel (i.e., the Investigator or delegate) and cannot be provided to the subjects to take home.

Compliance with treatment (%) will be always 100% if treatment is administered at each visit (12 in total), from Week 1 D1 to Week 6 D40.

Study treatment is considered administered if answered 'Yes' to the question "LSD / Placebo administered?" in the "Study Drug Administration" CRF section. Study drug administration will be collected at each visit.

If Compliance with treatment (%) is different from 100%, it will be derived according to the following formula:

Total compliance (%) = (Total number of doses taken / Total number of expected doses) x 100\*,  
where:

*Total number of doses taken = Total number of expected doses – Total number of missed doses.*

*Total number of expected doses = 12 (number of doses to be administered at all 12 visits).*

*Total number of missed doses = number of doses not administered (study treatment is considered NOT administered if answered 'No' to the question "LSD / Placebo administered?" in the "Study Drug Administration" CRF section).*

In case of “Special Situation” at any visit (answer to “Were there any special situation with the study drug?” is [Yes]), the compliance will be not calculated, and the following information will be provided:

- Number of subjects with at least one Special Situation;
- Number of Special Situations;

and number of patients with ticked box 'Yes' to any of the following:

- Medication error or incorrect drug administration;
- Overdose (exceeds the protocol-specified maximum);
- Deliberate abuse;
- Deliberate misuse;
- Drug interaction;
- Occupational exposure.

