#### **10.4 EXPOSURE TO STUDY TREATMENT**

Treatment duration (days) as defined in section 8.5 will be listed and summarized on SAF using descriptive statistics for continuous variables, by treatment group

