### 13.1.6 Layout T6

Study MMED007 - Deliverables: <Deliverables>

Table <Number of table>

<Title>

Analysis set: <analysis set>

	MM-120 N=xx	Placebo N=xx
Exposure (days)	xx	xx
n	xx.x	xx.x
Mean	xx.x	xx.x
Standard Deviation	xx.x	xx.x
Standard Error	xx.x	xx.x
Median	xx.x	xx.x
Q1 , Q3	xx.x, xx.x	xx.x, xx.x
Min , Max	xx.x, xx.x	xx.x, xx.x

Program: [program\\_name.sas](#), Produced on yyyy-mm-dd hh:mm (CET),

Snapshot date: yyyy-mm-dd, Draft/final

Page x of x

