### 13.1.11 Layout T11

Study MMED007 - Deliverables: <Deliverables>

Table <Number of table>

<Title>

Analysis set: <analysis set>

	MM-120 N=xx N (%)	Placebo N=xx N (%)
Compliance (%) categories		
100% (12/12)	xx (yy.y)	xx (yy.y)
91.7% (11/12)	xx (yy.y)	xx (yy.y)
83.3% (10/12)	xx (yy.y)	xx (yy.y)
etc.	xx (yy.y)	xx (yy.y)
Number of subjects with at least one Special Situation	xx (yy.y)	xx (yy.y)
Number of Special Situations	xx	xx
Special situation*:		
Medication error or incorrect drug administration	xx (yy.y)	xx (yy.y)
Overdose	xx (yy.y)	xx (yy.y)
Deliberate abuse	xx (yy.y)	xx (yy.y)
Deliberate misuse	xx (yy.y)	xx (yy.y)
Drug interaction	xx (yy.y)	xx (yy.y)
Occupational exposure	xx (yy.y)	xx (yy.y)

\*Percentages are computed on "Number of Special Situations"

Program: [program\\_name.sas](#), Produced on yyyy-mm-dd hh:mm (CET),

Snapshot date: yyyy-mm-dd, Draft/final

Page x of x

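### The SAP's exposure summary drops the dose count that Protocol 13.4 requires, and the compliance table that largely replaces it leaves out subjects with a Special Situation

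*SAP*

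**What the plan says.** **Exposure.** Protocol 13.4 first defines treatment duration, first to last dose inclusive, summarised on the SAF. It then adds a second measure: "The total number of doses received by a subject during the double-blind treatment period will be summarized by treatment group for the SAF". SAP 8.5 gives duration only: "Exposure information will be expressed in terms of treatment duration (days) derived as the number of days from the date of first dose". The formula is "Study treatment end date - Study treatment start date +1". SAP 10.4 follows: "Treatment duration (days) as defined in section 8.5 will be listed and summarized on SAF using descriptive statistics for continuous variables, by treatment group". Output EXP (12.3.1), table T6 and listing L7 carry days and no dose count. Appendix D lists twelve changes from the protocol's analyses, and this is not among them.

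**Compliance.** The SAP handles dose counts here. Section 8.6 fixes the expected number at 12 and derives doses taken as 12 minus the visits answered No. Output COMPLSP (table T11) counts SAF subjects per arm at 12/12, 11/12, 10/12 and so on. Listing L8 prints doses taken per subject.

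**The exception.** If a subject has a Special Situation at any visit, "the compliance will be not calculated, and the following information will be provided". The types range from medication error and overdose to drug interaction and occupational exposure. Section 8.6 asks for the number of patients with each type, but the T11 footnote divides by the number of situations.

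**The concern.** Adverse events and efficacy are read against the exposure actually achieved. For a drug given every 3 to 4 days, with a half-life of 2.9 h at this dose (Protocol 1.4.2), the number of doses is the more informative measure, and the protocol asks for it by name. Days from first to last dose cannot show gaps in between. If the dose count is absent from the exposure table and incomplete in the compliance table, the study report would lack a full by-arm summary of doses received, and nothing in the SAP would tell the reader that a protocol-specified summary had been dropped.

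**Working it through.** **Inputs.** Twelve expected doses (SAP 8.6). Nominal dosing days 1, 5, 8, 12, 15, 19, 22, 26, 29, 33, 36 and 40 (SAP 10.12.1.1). Duration = last dosing day − first dosing day + 1 (SAP 8.5). Compliance = doses taken / 12 × 100 (SAP 8.6).

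**1. The plan's own figures.** 12/12 = 100.0%, 11/12 = 91.7% and 10/12 = 83.3%, as printed in T11. Because the denominator is constant, the T11 categories are a frequency distribution of doses received.

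**2. What each table shows.**

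| Dosing pattern | Doses | Duration (T6) | T11, no Special Situation | T11, any Special Situation |
|---|---|---|---|---|
| All 12 | 12 | 40 − 1 + 1 = 40 | 12/12 = 100.0% | not calculated |
| One interior dose missed | 11 | 40 − 1 + 1 = 40 | 11/12 = 91.7% | not calculated |
| Last dose missed | 11 | 36 − 1 + 1 = 36 | 11/12 = 91.7% | not calculated |
| Days 1 and 40 only | 2 | 40 − 1 + 1 = 40 | 2/12 = 16.7% | not calculated |
| Stopped after Day 5 | 2 | 5 − 1 + 1 = 5 | 2/12 = 16.7% | not calculated |

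Duration registers early stopping but no interior gap. T11 separates subjects by dose count, except in the last column. There the subject appears in the Special Situation rows, and the dose count can be read only from L8.

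**3. The percentage base.** Take, for illustration, one subject with two situations of the same type in an arm of the planned 26. The patient count is 1. The T11 footnote gives 1/2 = 50%; the SAF N gives 1/26 = 3.8%. The first figure is neither a share of patients nor a share of situations, since both situations were of that type.

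**4. How doses are counted.** Suppose a subject withdraws after dose 2. If the ten later visits are each answered No, the 8.6 formula gives 12 − 10 = 2 doses (16.7%). If those visits have no form, it gives 12 − 0 = 12 doses (100%). The documents do not say how such visits are completed, so the second case is an assumption. Counting Yes answers gives 2 either way.

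**The case against.** The strongest reply is that the protocol's requirement is largely met under another heading. T11 is produced by arm on the SAF, its categories are dose counts, and Protocol 13.4 asks for the count to be summarised without prescribing a mean or median for it. The title of output COMPLSP says openly that some subjects have no calculated compliance. First-to-last duration is the protocol's own first measure, so using it is no departure. All of this stands. What it does not answer is the gap for Special Situation subjects, the inconsistent percentage base and the missing entry in Appendix D.

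The reply also disposes of four stronger readings that a reader might draw:

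- *A subject with 2 of 12 doses cannot be told from one with all 12.* This is true of T6 alone. T11 shows 2/12 when there is no Special Situation, and L8 lists the count. The Day 1 and Day 40 pattern also needs ten consecutive missed doses and then the last one given.
- *Subjects with irregular dosing are removed from the compliance table.* A missed dose is not on the Special Situation list, so subjects who simply miss doses stay in the T11 categories.
- *The rule removes 3.8% of an arm.* That is 1/26, the share of one subject in a planned arm. The documents give no rate of Special Situations.
- *Efficacy conclusions are affected.* The primary analysis is by intention to treat on the full analysis set (SAP 10.7) and uses neither duration nor dose count.

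**Conclusion.** The point holds, and it is minor. The SAP omits a summary that the protocol specifies, and does not log the omission. The table that largely replaces it is incomplete by rule for every subject with a Special Situation, including types such as drug interaction or occupational exposure that need not alter the number of doses taken. The T11 percentages for patient counts rest on the wrong base. How many subjects are affected cannot be estimated from the documents; it could be none. The consequence is confined to exposure and compliance reporting, with no effect on the primary test or any other efficacy estimate.

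**What to change.** - **SAP 8.5, 10.4 and EXP/T6:** add total number of doses received, defined as the number of visits at which the study drug administration question is answered Yes. Give descriptive statistics by arm for every SAF subject. The range is 1 to 12, since SAF membership requires study drug.
- **SAP 8.6:** calculate compliance for all SAF subjects from the same count, and report Special Situations alongside it, not in its place.
- **T11:** base the percentages for patients with each type of situation on the SAF N.

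L8 already lists the count, so L7 need not change. The cost is a few lines of SAP text, one extra row block in T6 and one changed footnote in T11. The data are already collected at each visit in the study drug administration section of the CRF. The same edit can correct the pointer in 10.5 to a Section 4.2.1, which is not in the SAP's table of contents.

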### **8.6 COMPLIANCE WITH STUDY TREATMENT**

The IMP will be administered at the clinic under supervision of study personnel (i.e., the Investigator or delegate) and cannot be provided to the subjects to take home.

Compliance with treatment (%) will be always 100% if treatment is administered at each visit (12 in total), from Week 1 D1 to Week 6 D40.

Study treatment is considered administered if answered 'Yes' to the question "LSD / Placebo administered?" in the "Study Drug Administration" CRF section. Study drug administration will be collected at each visit.

If Compliance with treatment (%) is different from 100%, it will be derived according to the following formula:

Total compliance (%) = (Total number of doses taken / Total number of expected doses) x 100\*,  
where:

*Total number of doses taken = Total number of expected doses – Total number of missed doses.*

*Total number of expected doses = 12 (number of doses to be administered at all 12 visits).*

*Total number of missed doses = number of doses not administered (study treatment is considered NOT administered if answered 'No' to the question "LSD / Placebo administered?" in the "Study Drug Administration" CRF section).*

In case of “Special Situation” at any visit (answer to “Were there any special situation with the study drug?” is [Yes]), the compliance will be not calculated, and the following information will be provided:

- Number of subjects with at least one Special Situation;
- Number of Special Situations;

and number of patients with ticked box 'Yes' to any of the following:

- Medication error or incorrect drug administration;
- Overdose (exceeds the protocol-specified maximum);
- Deliberate abuse;
- Deliberate misuse;
- Drug interaction;
- Occupational exposure.

## 8.7 TRIAL DISCONTINUATION

Subjects with premature trial termination are identified as those with answer 'No' to the question 'Did the subject complete the study?' in the “Termination Form” CRF section.

The reasons that can be associated with the trial discontinuation are:

- Lost to follow-up;
- Death;
- COVID-19 related;
- Other (to be specified).

## 8.8 EFFICACY ENDPOINTS

### 8.8.1 Primary endpoint

The primary endpoint is the mean change from baseline in ADHD symptoms, based on the evaluation of the AISRS change from baseline to Week 6.

The AISRS total score consists of 18 items from the original ADHD-RS, which were derived based on DSM-5 criteria for ADHD. The ADHD-RS includes 9 items that address symptoms of inattention and 9 items that address symptoms of impulsivity and hyperactivity. Each item will be rated from 0 to 3. The AISRS total score can range from 0 to 54. A higher score corresponds to a worse severity of ADHD.

## 8.9 SECONDARY ENDPOINTS

### 8.9.1 ADHD related endpoints

- Key secondary endpoint: change in AISRS from baseline to 1 week (Week 2, pre-dose, as per Schedule of assessments 2.1.2) after 2 doses of treatment;
- Occurrence of subjects who experience at least a 1-point decrease in the CGI-S (improvement). The change in CGI-S from baseline to Week 2 and Week 6 will be categorized as improved or worsened/ no change and will be evaluated as dichotomous variable:

$$CGI - S = \begin{cases} \text{Improved if } (\text{Difference between week 2/6 and baseline}) < 0 \\ \text{No change or Worsened if } (\text{Difference between week 2/6 and baseline}) \geq 0 \end{cases}$$

- Change from baseline in CGI-S after 1 week (Week 2-predose) and 6 weeks (Week 6) of treatment;
- Change from baseline to each timepoint (see Section 10.8.2.2) in subject self-assessment by the Adult ADHD Self-Report Scale (ASRS) and Connors' Adult ADHD Rating Scale (CAARS-L-SR).

The CAARS-L-SR is a 66-item measure of ADHD symptoms. Responses are scored on a 4-point scale, where 0 = not at all, 1 = just a little, 2 = pretty much, and 3 = very much. Item scores are summed to three main scores which are then transformed using population-derived age- and sex-adjusted norm values to a T-score. A T-score < 60 indicates no ADHD. A T-score of 60-64 indicates borderline ADHD. A T-score of > 64 indicates ADHD.

The ASRS has 18 questions, which address ADHD symptoms in adults. It uses a scale that ranges from 0-4 based on the individuals mark in either "never, rarely, sometimes, often, very often" column for a possible total score of 72. Each column is used to describe the severity of the individual's symptoms based on the question asked. If four or more answers are scored "positive" then a high consistency of ADHD will be indicated and further follow-up with a licensed clinician is necessary.

These data are derived from "AISRS", "CGI-S" and "Subject Reported Outcomes" CRF sections (see Section 2.1.2 for time points).

### 8.9.2 Pharmacokinetic endpoints

PK samples will be collected at pre-dose, hours 0.5, 1, 2, 3, 4, and 6 post-dose (at "Week 1 D1", first drug administration visit). The actual date and time of collection of each sample is recorded on the "Pharmacokinetics" CRF section.

- $C_{max}$ , Maximum observed drug concentration
- $t_{max}$ , Time to reach  $C_{max}$
- $AUC_{0-t}$ , Area under the concentration-time curve from time zero to the measurable concentration time  $t$
- $t_{1/2}$ , Terminal elimination half-life

AUC will be calculated using trapezoidal rule. Missing values will be imputed with linear interpolation of the non-missing values that precede and follow the missing one(s). For details of PK endpoints definition and analysis, refer to Section 10.9.

### 8.9.3 Acute effects (Pharmacodynamic) endpoints

- 5 Dimensions of Altered States of Consciousness scale (5D-ASC). The 5D-ASC scale is a visual analog scale consisting of 94 items. The instrument is constructed of five scales, and allows assessing mood, anxiety, derealization, depersonalization, changes in perception, auditory alterations, and reduced vigilance. Each item of the scale is scored on a 0-100 mm VAS;
- Mystical Experience Questionnaire (MEQ), drug effect Visual Analog Scale (VAS).

The MEQ is a 30-item questionnaire rated on a six-point scale. Data on each domain scale is expressed as a percentage of the maximum possible score.

A series of single item VAS is used: "any drug effect", "good drug effect", "bad drug effect", "drug liking", "fear", "nausea", "alteration of vision", "alteration of sense of time", and "the boundaries between myself and my surroundings seem to blur".

These data are derived from “5D-ASC”, “MEQ-30” and “VAS” CRF sections (see Section 2.1.2 for time points).

## 8.10 EXPLORATORY ENDPOINTS

Sleep quality/duration rating evaluated based on daily diary entries (“Sleep Quality” CRF section) and assessment is specified in Section 2.1.1.

The respondent marks, an integer score from 0 to 10, are defined according to the following five categories:

0 = terrible,  
1–3 = poor,  
4–6 = fair,  
7–9 = good,  
10 = excellent

## 8.11 SAFETY ENDPOINTS

The evaluation of safety of study drug will be done considering the following variables:

- Adverse events ('Adverse Event' CRF section);
- Safety laboratory evaluation and Urine pregnancy testing ('Blood sample' and [REDACTED] sections of the CRF);
- Vital signs, i.e. supine blood pressure, body temperature, heart rate, respiratory rate ('Vital signs' CRF section);
- 12-lead safety ECG ('12-Lead ECG' CRF section);
- Columbia-Suicide Severity Rating Scale (C-SSRS, 'C-SSRS SLV' CRF section).

### 8.11.1 Adverse events (AEs)

Adverse events (AEs) data are collected in the "Adverse Events" CRF sub-section of the "Medical Events" section. An Adverse Event is any untoward medical occurrence in a clinical trial which does not necessarily have a causal relationship with this treatment.

As a general rule, the variable of interest will be the occurrence of at least one AE.

#### 8.11.1.1 Treatment-emergent adverse events (TEAEs)

Treatment-emergent adverse events are any event with onset date/time between the study treatment start date and the study treatment end date, limits included.

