### **10.12.1 Adverse events**

Adverse events (AEs) will be summarized for treatment emergent adverse events (TEAEs). TEAEs are defined as AEs that occur on or after the day of the first dose. MedDRA terminology will be used to classify all AEs with respect to system organ class (SOC) and preferred term (PT).

A summary of subjects with TEAEs will be presented for each treatment group. The summary will include counts and percentages for subjects who experience at least one AE, overall and by SOC and PT. This will be repeated for severe TEAEs, related TEAEs and serious TEAEs. Severity will be captured as Grade 1 through Grade 5 with Grades 3-5 categorized as severe. Related will be captured

as: none, unlikely, possibly or probably, with related = possibly or probably. Serious will be captured with the standard serious adverse event (SAE) criteria.

The summary tables will be presented in descending order according to the incidence in the 'All' group (e.g., SOC and PT within each SOC with the highest number of occurrences will appear first). Equal frequency of different SOC/PTs will be sorted in alphabetical order of the SOC/PT.

Subjects who report the same PT on multiple occasions will be counted once for the preferred term under the highest severity when summarizing by severity, under the closest relationship to the drug when summarizing by relationship, under most serious when summarizing by seriousness.

Separate summary tables by SOC and PT will be provided for: TR-TEAEs, SAEs, and AEs leading to premature treatment discontinuation.

Individual subject listings will be provided on SAF.

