#### **10.12.1.1 Subgroup analysis**

TEAEs, SAEs, AEs related to the study drug and AEs leading to premature treatment discontinuation will be tabulated on SAF by preferred term (PT) by treatment phase as follows:

- **Days of dosing:** all AEs occurred on same date/visit of treatment but only during or after administration of study drug (with time on or after treatment administration). Week 1 D1 (Dose 1), Week 1 D5 (Dose 2), Week 2 D8 (Dose 3), Week 2 D12 (Dose 4), Week 3 D15 (Dose 5), Week 3 D19 (Dose 6), Week 4 D22 (Dose 7), Week 4 D26 (Dose 8), Week 5 D29 (Dose 9), Week 5 D33 (Dose 10), Week 6 D36 (Dose 11), Week 6 D40 (Last dose 12);

This information will be pooled in summary table, i.e. all AEs occurred on/after all doses: first, second etc. until last dose; as well as will be summarized separately, i.e. AEs occurred on/after each dose: on/after first dose, on/after second dose etc. and until on/after last dose.

- **Non-dosing days:** (a) all AEs with the date different from treatment administration date/visit defined above and until Week 10 Follow-up visit. (b) all AEs which occurred prior to study drug administration (with time before administered dose) on dosing days.

This information will be pooled in summary table, i.e. all AEs occurred between doses: first and second, second and third etc. until Week 10 Follow-up visit (EOS) or until Early Termination (ET) whatever comes earlier, as well as will be summarized separately, i.e. split by periods between doses: Dose 1 - Dose 2, Dose 2 - Dose 3, Dose 3 - Dose 4, Dose 4 - Dose 5, Dose 5 - Dose 6, Dose 6 - Dose 7, Dose 7 - Dose 8, Dose 8 - Dose 9, Dose 9 - Dose 10, Dose 10 - Dose 11, Dose 11 - Dose 12, Dose 12 | last administered Dose - EOS | ET.

In case of missing dates, the rules defined in Section 11.3.3 will be applied. In case of missing time of the AE or the treatment administration on the same day, the AE will be considered as occurred after the treatment administration, meaning will be summarized in 'Days of dosing' category.

Frequency statistics will be presented by treatment group. The summary tables will be presented in descending order according to their incidence in the active treatment group of 'Days of dosing' treatment phase (e.g., individual preferred term with the highest number of occurrences appear first) sorting ties alphabetically.

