### **11.1.1.3 Study treatment end date (EOT)**

This is the last day of study drug intake, which is the date reported in “Date of visit” field in section “Medical Events checks” (for each Visit form) when “LSD / Placebo administered” is ticked “Yes” in “Study Drug Administration” section.

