## 12.8 Safety endpoints

### 12.8.1 Adverse events

Output name	Display*	Title (Description)	Analysis set(s)**	Key deliverable	Mock layout	SAP section
AESOC	S	Summary of adverse events (AE) by system organ class (SOC) and individual preferred term (PT)	SAF		Layout T4	10.12.1
AEPT	S	Summary of adverse events (AE) by individual preferred term (PT)	SAF		Layout T8	

Output name	Disp lay*	Title (Description)	Analysis set(s)**	Key deliverable	Mock layout	SAP section
TEAESOC	S	Summary of treatment-emergent adverse events (TEAE) by system organ class (SOC) and individual preferred term (PT)	SAF	Yes	Layout T4	
TEAEPT	S	Summary of treatment-emergent adverse events (TEAE) by individual preferred term (PT)	SAF		Layout T8	
SAESOC	S	Summary of serious adverse events (SAE) by system organ class (SOC) and individual preferred term (PT)	SAF	Yes	Layout T4	
SAEPT	S	Summary of serious adverse events (SAE) by individual preferred term (PT)	SAF		Layout T8	
SARSOC	S	Summary of serious adverse reaction (SAR) by system organ class (SOC) and individual preferred term (PT)	SAF		Layout T4	
SARPT	S	Summary of serious adverse reaction (SAR) by individual preferred term (PT)	SAF		Layout T8	
AEPDSOC	S	Summary of adverse events leading to premature discontinuation of study drug by system organ class (SOC) and individual preferred term (PT)	SAF		Layout T4	
AEPDPT	S	Summary of adverse events leading to premature discontinuation of study drug by individual preferred term (PT)	SAF		Layout T8	
AESRSOC	S	Summary of adverse events related to the study drug by system organ class (SOC) and individual preferred term (PT)	SAF		Layout T4	

Output name	Disp lay*	Title (Description)	Analysis set(s)**	Key deliverable	Mock layout	SAP section
AESRPT	S	Summary of adverse events related to the study drug by individual preferred term (PT)	SAF		Layout T8	
DEATH	S	Summary of deaths and causes of death	SAF		Layout T9	
LAE	L	Subject listing of adverse events	SAF		Layout L10	
LUAR	L	Subject listing of Unexpected Adverse Reaction (UAR) and Suspected Unexpected Serious Adverse Reaction (SUSAR)	SAF		Layout L10	
LSAE	L	Subject listing of serious adverse events (SAE)	SAF		Layout L10	
LSAR	L	Subject listing of serious adverse reaction (SAR)	SAF		Layout L10	
LAEPD	L	Subject listing of adverse events leading to premature discontinuation of study drug	SAF		Layout L10	
LDEATH	L	Subject listing of deaths	SAF		Layout L24	

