### 12.8.1.1. Subgroup analysis

Output name	Disp lay*	Title (Description)	Analysis set(s)**	Key deliverable	Mock layout	SAP section
TEAEPTTP	S	Summary of treatment-emergent adverse events (TEAE) by individual preferred terms (PT) by treatment phase.	SAF	Yes	Layout T27	
SAEPTTP	S	Summary of serious adverse events (SAE) by individual preferred terms (PT) by treatment phase.	SAF	Yes	Layout T27	10.12.1.1

Output name	Display*	Title (Description)	Analysis set(s)**	Key deliverable	Mock layout	SAP section
AEPDPTTP	S	Summary of adverse events leading to premature discontinuation of study drug by individual preferred terms (PT) by treatment phase.	SAF		Layout T27	
AESRPTTP	S	Summary of adverse events related to the study drug by individual preferred terms (PT) by treatment phase.	SAF		Layout T27	

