### 13.1.4 Layout T4

Study MMED007 - Deliverables: <Deliverables>

Table <Number of table>

<Title>

Analysis set: <analysis set>

<Medical history/Concomitant diseases>

System Organ Class / Preferred Term	MM-120 N=xx N (%)	Placebo N=xx N (%)	All N=xx N (%)
ALL SYSTEM ORGAN CLASSES			
Total number of subjects with at least one <medical and psychiatric events   AE>	xx (yy.y)	xx (yy.y)	xx (yy.y)
System Organ Class 1 <preferred term1> <preferred term2>	xx (yy.y) xx (yy.y) xx (yy.y)	xx (yy.y) xx (yy.y) xx (yy.y)	xx (yy.y) xx (yy.y) xx (yy.y)
System Organ Class n <preferred term1> <preferred term2>	xx (yy.y) xx (yy.y) xx (yy.y)	xx (yy.y) xx (yy.y) xx (yy.y)	xx (yy.y) xx (yy.y) xx (yy.y)

System Organ Class and Preferred terms are based on MedDRA 25.1 dictionary.

Program: [program\\_name.sas](#), Produced on yyyy-mm-dd hh:mm (CET),

Snapshot date: yyyy-mm-dd, Draft/final

Page x of x

Note for programmer: display medical history and concomitant diseases in separate pages.

Please use 'System Organ Class and' only in tables by SOC and PT and not in those only by PT.

Please add footnote 'Treatment-emergent adverse events are events with onset date/time between the study treatment start date and the study treatment end date, limits included.' In the tables with treatment-emergent AEs.

Please add footnote 'A Serious Adverse Reaction (SAR) is a serious adverse event that is determined to be related to the study treatment' to the table with Summary of serious adverse reaction (SAR) by system organ class (SOC) and individual preferred term (PT).

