### 13.2.11 Layout L10

Study MMED007 - Deliverables: <Deliverables>

Listing <Number of listing>

<Title>

Analysis set: <analysis set>

Subject ID	Active Treatment	System organ class/ Preferred term/ Reported term	Start date/ Time/ Study Day*	End date/ Time/ Duration (days)	Treatment Emergent**	Serious	Severity	Relation. to study drug	Action Taken With Study drug		Outcome
									With Study drug	Outcome	
xxx	xxx	xxxxxx/ xxxxxx/ xxxxxx	ddmmyy/ yyy/ Hh:mm	ddmmyyyy/ Hh:mm	Yes/No	No/Yes: xxxx	xxxx	xxxx	xxxx	xxxx	xxxx

\*Study day is the day of the event relative to the treatment start date.

\*\*Treatment-emergent adverse event is any event with onset date/time between the study treatment start date and the study treatment end date, limits included.

System Organ Class and Preferred terms are based on MedDRA 25.1 dictionary.

Program: [program\\_name.sas](#), Produced on yyyy-mm-dd hh:mm (CET),

Snapshot date: yyyy-mm-dd, Draft/final

Page x of x

*Note for Programmer: Severity = Intensity of AE.*

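### The SAP gives two conflicting windows for treatment-emergent adverse events, and section 10.12.1 contradicts the SAP's own relatedness and intensity rules

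*SAP*

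**What the plan says.** **Window.** SAP 8.11.1.1: "Treatment-emergent adverse events are any event with onset date/time between the study treatment start date and the study treatment end date, limits included". SAP 11.1.1.3 on the end date: "This is the last day of study drug intake". The footnote of Layout T4 repeats the closed window ("Treatment-emergent adverse events are events with onset date/time between the study treatment start date and the study treatment end date, limits included"), as does that of Layout L10 ("Treatment-emergent adverse event is any event with onset date/time between the study treatment start date and the study treatment end date, limits included"). The Layout L24 footnote applies it to deaths.

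SAP 10.12.1 has a different rule: "TEAEs are defined as AEs that occur on or after the day of the first dose". It sets no upper limit.

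SAP 10.12.1.1 splits TEAEs by treatment phase, and its last non-dosing interval is "Dose 12 | last administered Dose - EOS | ET". The matching output in 12.8.1.1, TEAEPTTP, is titled "Summary of treatment-emergent adverse events (TEAE) by individual preferred terms (PT) by treatment phase" and is marked as a key deliverable. The Layout T27 footnote expands ET as end of treatment, whereas 10.12.1.1 and the abbreviation list use it for Early Termination.

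**Relatedness.** SAP 8.11.1.4 and 8.11.1.8 count possibly, probably and definitely related events. The causality scale in protocol 7.7 also has a definite category. SAP 10.12.1 lists four categories without it and counts only possibly and probably.

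**Severity.** SAP 8.11.1.2 has mild, moderate and severe, and the Layout L10 note equates severity with intensity. SAP 10.12.1 uses Grades 1 to 5, with 3 to 5 as severe, and gives no mapping.

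**Protocol.** Sections 12.1 and 13.6.7.1 also treat worsening of a pre-existing condition since treatment start as emergent. Neither SAP definition keeps this. The protocol's onset clause refers to the time after the intervention phase, which must be a slip for after its start.

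**The concern.** The TEAE counts depend on which section the programmer follows. Tables built on 10.12.1 would show open-window counts above a footnote describing the closed window.

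Under 8.11.1.1, two kinds of event stop being treatment-emergent: everything that starts in follow-up, and an event that starts on a day between doses and ends treatment before the next dose. The second kind bears directly on tolerability, which is a stated objective.

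Following 10.12.1 literally has a separate cost: the events most firmly attributed to the drug fall out of the related-TEAE summary, and severe has no usable rule for data recorded at three levels.

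**Working it through.** The plan states no figure for this point, so the check compares the sections and then counts days and tables.

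**1. Where an event falls**

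| Onset | SAP 8.11.1.1 | SAP 10.12.1 |
|---|---|---|
| Dosing day, after the dose | TEAE | TEAE |
| Between doses, another dose follows | TEAE | TEAE |
| Between doses, treatment then stops | not a TEAE | TEAE |
| Follow-up after the final dose | not a TEAE | TEAE |

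**2. The last interval of the phase table.** Section 10.12.1.1 puts an event with onset on the last-dose date, after dosing or with time missing, under dosing days. An event earlier that day belongs to the preceding interval. Any later onset is outside 8.11.1.1. The final interval therefore cannot contain a TEAE under the closed window.

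**3. Days outside the closed window, all 12 doses taken.** The planned last dose is Day 40 (10.12.1.1). Follow-up is 4 weeks after the last treatment visit (SAP 2.1.1), so 40 + 28 = Day 68; the target in SAP Tables 2 and 3 is Day 70. Share outside = (follow-up day − 40) / follow-up day.

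- Day 68: 28/68 = 41.2%
- Day 70: 30/70 = 42.9%
- Day 68 with the ±3-day window of protocol 6.2.5: 25/65 = 38.5% to 31/71 = 43.7%
- Day 70 with the same window: 27/67 = 40.3% to 33/73 = 45.2%

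**4. Early stoppers.** The share rises as the last dose moves earlier. Assuming observation to Day 70, a last dose on Day 22 leaves 48/70 = 68.6% outside. A subject stopping after the Day 1 dose has a one-day window, so an event starting on Day 2 that ends treatment is not a TEAE.

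**5. Tables.** SAP 12.8.1 lists 13 adverse event summary tables and 12.8.1.1 lists 4, so 17 in all. Three are TEAE tables: TEAESOC, TEAEPT and TEAEPTTP. Four are key deliverables: TEAESOC and TEAEPTTP, which depend on the TEAE flag, and SAESOC and SAEPTTP, which are restricted to serious events. A non-serious event starting after the last-dose date is in none of the four under 8.11.1.1. It remains in the all-AE tables, in the related-AE and discontinuation tables where they apply, and in the listings.

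**6. Promised summaries.** Section 10.12.1 announces severe, related and serious TEAE summaries. Section 12.8.1 lists no TEAE-labelled table for any of these. Its related-AE tables share their wording with 8.11.1.4, which includes definitely related events.

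**7. Is it resolved elsewhere?** The version history (Appendix B) and the list of changes from the protocol (Appendix D) do not mention the TEAE definition, the relatedness rule or the severity scale.

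**The case against.** The closed window is the SAP's more frequent choice. It is in 8.11.1.1 and three footnotes, it matches the treatment period in 11.1.1.5, and the laboratory section (8.11.3.2) ends its treatment-emergent window at treatment discontinuation. On that view 10.12.1 is leftover text, and aligning one sentence would do. Layout T27 also serves three outputs that are not TEAE tables, so its last interval need not imply an open window. A short window can be argued from the pharmacology: protocol 1.4.2 and 1.4.3 give a half-life of 2.9 h and effects lasting 6 h at 20 µg, so five half-lives are 5 × 2.9 = 14.5 h. The 41% to 43% is calendar time, not events. No safety inference is planned, the key-deliverable mark appears to denote the topline set, and every omitted event is still reported somewhere.

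Most of this stands as a limit on size. An on-treatment window is a legitimate choice, but the SAP has not made it: it states two rules and plans TEAEs by phase through end of study or early termination. The pharmacology does not settle the window either. A window that closes on a calendar date has no stated lag, and protocol 7.4.2 reports a moderate headache needing acetaminophen the day after an LSD session. The protocol's adverse event definition may lead some worsenings to be recorded with their own onset date, which softens the missing worsening criterion but does not replace it. None of these arguments removes the relatedness or severity conflict.

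**Conclusion.** The point holds and should be fixed. The SAP has two incompatible TEAE windows, differing by 28 to 30 days for a subject who takes every dose (41% to 43% of the time from first dose to follow-up, or 38% to 45% with visit windows) and by more for early stoppers observed to the same day. These shares assume the planned dosing days. The number of events affected cannot be computed, because the documents give no adverse event rates.

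The relatedness and severity rules in 10.12.1 contradict 8.11.1.4 and 8.11.1.2. Taken literally, the first drops definitely related events from related TEAEs. The effect is on descriptive safety reporting only; no efficacy result or test is touched.

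**What to change.** - State one TEAE definition and use it in 8.11.1.1, 10.12.1 and the T4, L10 and L24 footnotes: onset, or worsening of a pre-existing condition, from first dose through end of study or early termination. This agrees with 10.12.1 and the phase table, and restores the protocol's worsening criterion.
- If an on-treatment view is wanted, add it as a further table with its lag after the last dose stated. Say whether the shorter laboratory window in 8.11.3.2 is deliberate.
- In 10.12.1, define related as possibly, probably or definitely (8.11.1.4), and severe as intensity Severe (8.11.1.2).
- Either add the severe, related and serious TEAE tables to 12.8.1 or delete them from 10.12.1.
- In the T27 footnote, expand ET as Early Termination.
- Correct the protocol's onset clause to after the start of the intervention, and record in Appendix D any definition that still differs from the protocol.

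The cost is SAP and footnote wording plus one changed flag in the adverse event dataset. Deriving worsening, and the extra tables if they are kept, add some programming. No new data are needed for the window, relatedness or severity corrections.
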